Despite the promising results, its efficacy in patients with acute severe manifestations, including organ-threatening cardiomyopathy and gastrointestinal involvement, remains under investigation. Additionally, while the efficacy of mepolizumab in ANCA-negative EGPA has been suggested by some studies, the MIRRA trial did not show a significant association between efficacy and ANCA status.

From March 2023, Mepolizumab 300 mg administered subcutaneously every 4 weeks has been approved in Italy as adjunctive therapy for patients aged 6 years and older with relapsed/remitting or refractory eosinophilic granulomatosis with polyangiitis (EGPA).

In clinical practice, the role of the otorhinolaryngologist is crucial in assessing the evolution of symptoms and naso-sinus signs in patients with EGPA and concomitant severe and uncontrolled CRSwNP.

Studies conducted in clinical practice, or 'real-life' studies, represent a fundamental tool for assessing the effectiveness of a therapeutic treatment. Our study aims to be one of the first to investigate the efficacy on the sino-nasal region of Mepolizumab 300 mg administered subcutaneously every 4 weeks in a real-life setting, thus contributing to an improvement in knowledge on the use of this drug in the management of EGPA.

OBJECTIVES

The *primary objective* of this study is evaluating the reduction of dimension of nasal polyps measured with Nasal Polyp Endoscopic Score (NPS)

The *secondary objective* is to evaluate the improvement in nasal symptoms and quality of life in the patient measured through symptom questionnaires, the improvements in terms of smell dysfunction and symptomatology related to eosinophilic otitis media; evaluate the need of surgery or systemic corticosteroids.

ENDPOINTS

Primary endpoint

The primary endpoints will be the Improvement of NPS score (indicative of polyps score reduction) at 12 months after start of therapy.

Secondary endpoints

- Improvement of SNOT-22 score (indicative of an improvement in quality of life)
- Improvement of VAS score for nasal obstruction
- Improvement of Nasal Congestion Score (NCS)
- Improvement of VAS score for smell;
- Improvement of sniffin' sticks score;
- Evaluate adherence to drug therapy with Mepolizumab 300, any suspension of the same and reasons for discontinuing treatment (lack of efficacy, complications reported, safety profile);
- Assess how many patients require FESS surgery and/or systemic steroids for sino-nasal symptoms during treatment;

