Considering NPS as a primary outcome a sample size of 52 patients achieves 80% power to reject the null hypothesis of zero effect size when the population effect size is 0.40 and the significance level (alpha) is 0.05. Anticipating a 20% drop-out rate, 65 patients should be enrolled to obtain the final sample size of 52 subjects. The sample size calculation was performed with a two-tailed Student's t test for paired data with PASS2025 statistical software v25.0.2.

Statistical Analysis.

The sample will be described in its clinical and demographic characteristics by descriptive statistics techniques. In depth, qualitative data will be expressed as absolute and relative percentage frequency, whilst quantitative variables by either mean and standard deviation (SD) or median and interquartile range (IQR), as appropriate. To verify the Gaussian distribution of quantitative variables, the Shapiro-Wilk test will be applied.

Fluctuations over time of NPS, NCS, VAS related to nasal obstruction, smell, sleeping disorders, rhinorrhea and craniofacial pain, nasal identification test by Sniffin' sticks, SNOT-22 questionnaire, will be assessed by repeated measurement analysis of variance or Friedman's nonparametric test, as appropriate. Correction for multiple pairwise comparisons will be performed by the Bonferroni test.

Fluctuations of the different parameters over time will be further represented by "violin plots" for quantitative variables or bar plots for qualitative/ordinal data, by using R packages "*ggpubr*", "*ggstatsplot*", "*ggplot2*", "*ggprism*" and "*ggsignif*", on both the overall sample and stratified for past surgery, asthma or ASA triad.

Potential predictors of clinical response at each time point will instead be assessed by univariable and multivariable logistic regression models with the "*rms*" R package. We will consider clinical and anamnestic variables and scores related to the immediately previous time-point (e.g., for 3-months model we will consider scores at 1-month visit).

Statistical significance will be set at a p-value <0.05 . Suggestive p values will be also reported ($0.05 \leq p < 0.10$). All analyses will be performed with R software version 4.2.0 (CRAN[®], R Core 2022, Wien, Austria).

SAFETY / REGULATORY MANAGEMENT OF ADVERSE EVENTS

Definitions for medicinal product(s)

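### The study is sized on a paired t test of NPS that the analysis section never names, and under the stated Bonferroni-corrected comparisons the 12-month contrast does not have 80% power

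*Protocol*

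**What the plan says.** Protocol, Endpoints: "The primary endpoints will be the Improvement of NPS score (indicative of polyps score reduction) at 12 months after start of therapy".

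Protocol, Sample size calculation: "Considering NPS as a primary outcome a sample size of 52 patients achieves 80% power to reject the null hypothesis of zero effect size". The calculation takes d = 0.40 and alpha = 0.05. The test is identified: "The sample size calculation was performed with a two-tailed Student's t test for paired data". Enrolment allows for losses: "Anticipating a 20% drop-out rate, 65 patients should be enrolled to obtain the final sample size of 52 subjects".

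Protocol, Statistical Analysis. The descriptive paragraph offers mean and SD or median and IQR, and ends: "To verify the Gaussian distribution of quantitative variables, the Shapiro-Wilk test will be applied". The next paragraph opens "Fluctuations over time of NPS, NCS, VAS related to nasal obstruction" and goes on through the other scores. It assigns all of them to repeated-measures ANOVA or Friedman's test, whichever suits, with a Bonferroni correction for pairwise comparisons. It does not say how many comparisons are corrected for, whether Shapiro-Wilk is run on visit scores, changes or residuals, or which result is the primary one.

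Protocol, Procedures: data are collected at baseline, 30 days and 3, 6, 9 and 12 months, so there are six time points.

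**The concern.** The endpoint and the sample size both point to one quantity, the within-patient change in NPS from baseline to month 12. The analysis section does not analyse that quantity on its own. It treats NPS as one of several scores followed over six visits, leaves open which of two omnibus tests will be used, and reaches month 12 only through corrected pairwise tests.

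Two things are at stake. First, the stated power belongs to a single uncorrected paired t test. If the 12-month result is read from a Bonferroni-corrected set, its power is lower by an amount that depends on an unstated number of comparisons. Second, the choice of test is left to the data. If the normality check is meant to make that choice, it responds mainly to NPS being a coarse whole-number score. A paired comparison depends instead on the distribution of the within-patient differences, whose mean is close to normal with 52 patients. Friedman's test, the likely outcome, gives no estimate of the 12-month change.

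**Working it through.** **Inputs from the protocol:** d = 0.40, two-sided alpha 0.05, 52 evaluable, 20% drop-out, six time points.

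**Assumptions (not in the protocol):** NPS takes whole numbers from 0 to 8. Visit SDs of 1.0–2.0 are used for the normality checks, and SD 1.5 with between-visit correlation 0.5 for the power simulation.

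**1. The plan's own figure.** Power of a paired t test is P(|T| > t_crit), with T noncentral t, df = n − 1 and noncentrality d√n.
- n = 52: 0.40 × √52 = 2.884; t_crit(51 df, 0.05) = 2.008; power 80.8%.
- n = 51 gives 79.99%, so 52 is the smallest n that reaches 80%.
- 52 / (1 − 0.20) = 65.

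Both stated figures reproduce.

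**2. The same contrast under Bonferroni.** Six visits give 6 × 5 / 2 = 15 pairs, or 5 comparisons against baseline.

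| Comparisons | Alpha for each | t_crit (51 df) | Power at n = 52 | Evaluable n for 80% | Enrolled at 20% drop-out |
|---|---|---|---|---|---|
| 1 | 0.05 | 2.008 | 80.8% | 52 | 65 |
| 5 | 0.01 | 2.676 | 58.5% | 77 | 97 |
| 15 | 0.00333 | 3.080 | 43.2% | 94 | 118 |

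**3. What the rank test costs.** I simulated whole-number NPS with a 0.6-point drop by month 12. The SD of the difference is 1.5 × √(2 × (1 − 0.5)) = 1.5, so d = 0.6 / 1.5 = 0.40 before rounding. Rounding adds about 1/12 to the variance at each visit: √(2.25 + 2/12) = 1.555, and 0.6 / 1.555 = 0.386. This is why the t test falls slightly below 80% here. There were 1,000 runs per course, n = 52.

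| Course of the drop | Paired t | Signed-rank | ANOVA | Friedman | t, 15 pairs | Signed-rank, 15 pairs |
|---|---|---|---|---|---|---|
| Linear | 79.1% | 77.8% | 75.5% | 69.6% | 38.2% | 33.5% |
| Early plateau | 77.8% | 77.2% | 79.1% | 74.4% | 40.1% | 36.0% |
| Late | 76.2% | 75.9% | 76.5% | 70.9% | 36.5% | 34.4% |

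Friedman lies 5 to 6 points below ANOVA and 3 to 10 points below the paired t test. The signed-rank test of the 12-month difference is within about 1 point of the t test. The 15-pair correction takes about 38 to 41 points off the t test. With a 2-point drop every method has 100% power.

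**4. How often Shapiro-Wilk rejects** (5% level, n = 52, 2,000 runs per setting except where noted).
- NPS at one visit: 99–100% at mean 5.5 (SD 1.0–2.0), 88–93% at mean 3 and 50–83% at mean 4 (SD 1.5–2.0).
- NPS at one or more of six visits: 100% in every course in step 3 (1,000 runs each).
- NPS change: 84% at SD 1.5, 40% at SD 2, 20% at SD 2.5.
- Other scores: SNOT-22 (0–110 assumed) 5–48%, VAS about 24%, Sniffin' Sticks identification 8%.

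**The case against.** The strongest reply is that several natural inferences go further than the text.

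- **Shapiro-Wilk decides the test.** A reader might infer this, but the sentence closes the descriptive paragraph, directly after the choice between mean/SD and median/IQR. Nothing ties it to the choice between ANOVA and Friedman in the next paragraph. This stands. What remains is that no other criterion is given, so the choice is either made by that test or has no rule.
- **Bounded scores almost always fail the test.** This holds for NPS by visit on the assumed scale. It does not hold generally for SNOT-22, VAS or Sniffin' Sticks, nor for NPS changes with a larger SD.
- **The result is only a p-value for some change at some visit.** The protocol does not support this. The corrected pairwise comparisons include baseline against month 12, and score levels will be summarised.
- **The rank method is what destroys the power.** It is not. The t test loses about as much under the same correction. A rank test of a coarse score is also defensible.
- **A statistical analysis plan may supply a change estimate with its interval.** That may be so, and the absence of that detail alone would not be a finding. But the protocol does state an analysis for NPS, and it is not the one that the sample size was computed for. That part stands whatever Shapiro-Wilk shows.

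**Conclusion.** The point holds as a mismatch between the sample size and the stated analysis. The 52 and 65 are correct for a single paired t test at 0.05, but the analysis section does not name that test. Under the analysis it does state, the baseline-to-month-12 contrast has about 59% power with 5 corrected comparisons or 43% with 15. These two figures use only the protocol's d, alpha and n; the number of comparisons is the one open input, so both are shown.

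The choice between ANOVA and Friedman is a smaller matter: at most about 10 points at d = 0.40 and nothing at a 2-point drop, under the assumed SD and correlation. Its main cost is that the method is left to the data and that Friedman, the likely result for NPS if normality is the criterion, gives no estimate of the change.

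A reader might infer that the study is too small and must enrol 97 or 118. That does not follow. If the 12-month contrast is named as the single primary test, no correction is needed for it and the planned size is adequate for d = 0.40.

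**What to change.** In Statistical Analysis, state that:

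- the single primary analysis is the mean within-patient change in NPS from baseline to month 12 with its 95% CI, by paired t test at two-sided 0.05 without multiplicity adjustment;
- the Wilcoxon signed-rank test of the same difference is a sensitivity analysis;
- Shapiro-Wilk does not select the primary test and serves only to choose mean/SD or median/IQR in the descriptive tables;
- the six-visit ANOVA or Friedman test and its Bonferroni-corrected pairs are secondary, with the number of comparisons given.

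This brings the analysis into line with the protocol's own calculation. It costs a few sentences in one section, with no new data and no change to the 52 or 65. Because part of the cohort is retrospective, the wording should be fixed before any NPS results are analysed.

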Patients receiving Mepolizumab 300 are generally evaluated in normal clinical practice at baseline and 30 days after first administration for an early re-evaluation. Subsequently, follow-up is continued with clinical re-evaluation every 3 months in the first year of treatment. Due to this reason, all participating centers will be asked to retrieve the clinical data of the visits performed at 30 days since the beginning of therapy and at 3,6,9 and 12 months.

As well, all centers will be required to provide data about any discontinuation of Mepolizumab due to adverse effects, intolerance to the drug, or related to its inefficacy. We will finally record any sino-nasal surgical treatment during treatment.

Variables

Data from the baseline clinical evaluation and follow-up visits will include a complete sensitized medical history and radiological or laboratory data carried out as normal practice.

In depth, we will collect:

- Anthropometric characteristics (age, height, gender, body mass index);
- Clinical characteristics (occupational exposure to particulate, exposure to cigarette smoke, allergies and sensitization to various allergens, presence of comorbidities, need for hospitalization for asthma and/or access to the emergency room in recent years);
- Assessment of symptoms and quality of life through validated questionnaires such as SNOT-22, Total Nasal-Symptom Score-VAS and Nasal Congestion Score (NCS);
- Nasal endoscopic staging: Nasal Polyp Score (NPS);
- Radiological extension of the CRSwNP: Lund-MacKay Score (LMS);
- Laboratory data (differential count of peripheral leukocytes, neutrophils, lymphocytes, monocytes, eosinophils, basophils), determination of total and specific IgE;
- Type of inflammation gathered from the result of non-invasive tests such as nasal cytology;
- Medications regularly taken by the patient for CRSwNP, and for comorbidities

(asthma, allergic rhinitis, etc.);

- Surgical history and any surgical treatment carried out before and during Mepolizumab therapy;
- Adverse reactions reported during drug treatment.

Sample size calculation

Based on the most recent literature, retrieved from the findings of preliminary phase III studies on Mepolizumab in the treatment of severe CRSwNP, a significant reduction NPS and SNOT-22 was observed. We therefore expect in our real-life experience a significant mean decrease at 12 months. Hence, hypothesing to assess a similar small effect size [$d = (\mu_1 - \mu_2) / \sigma$].

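### The repeated-measures ANOVA and Friedman's test named for all scores drop any patient with one missed visit; a mixed model on all available visits would keep partial data, though it would not cure informative drop-out

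*Protocol*

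**What the plan says.** The primary endpoint (Protocol, Endpoints) is "Improvement of NPS score (indicative of polyps score reduction) at 12 months after start of therapy". Under Procedures, patients are "evaluated in normal clinical practice at baseline and 30 days after first administration", and centres are to "retrieve the clinical data of the visits performed at 30 days since the beginning of therapy and at 3,6,9 and 12 months". That makes six time points. The design is observational and multicentre, partly retrospective and partly prospective.

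Under Statistical Analysis, changes over time in NPS, SNOT-22, NCS, the VAS scores and the Sniffin' Sticks test "will be assessed by repeated measurement analysis of variance" or by Friedman's test, whichever suits the data. The follow-up rule is: "Correction for multiple pairwise comparisons will be performed by the Bonferroni test". The section does not say which patients enter each pairwise comparison.

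The Sample size calculation rests on a two-sided paired t test with effect size 0.40, alpha 0.05 and 80% power. It continues: "Anticipating a 20% drop-out rate, 65 patients should be enrolled to obtain the final sample size of 52 subjects".

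**The concern.** In their classical forms, repeated-measures ANOVA and Friedman's test work on complete rows: a patient without a value at any one of the six visits leaves the test altogether. The primary endpoint needs only baseline and month 12, yet a missed 9-month visit can exclude a patient who has both.

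The methods suit this study poorly. The visits are those that routine care happens to deliver, and some are read from charts after the fact, so isolated gaps are to be expected. The sample size makes no provision for them, because its 20% covers only patients who drop out.

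Two things are at stake. The analysed sample can fall below the 52 on which the power rests. And the patients with complete rows may differ from the rest, so the estimated change may be biased. The visits already collected from the 65 − 52 = 13 expected drop-outs would not be used at all.

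**Working it through.** **Inputs from the protocol.** d = 0.40, two-sided alpha 0.05, paired t test, 52 evaluable and 65 enrolled, 20% drop-out (Sample size calculation); six visits, of which four lie between baseline and month 12 (Procedures).

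**Inputs that are assumptions.** The chance m that a patient still followed at month 12 misses a given intermediate visit, taken as independent across visits. The protocol gives no such rate, so a range is shown.

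**1. The plan's own figures.** Power = P(|T| > t(0.975, n − 1)), where T is noncentral t with n − 1 degrees of freedom and noncentrality d√n.
- n = 51: 79.99%.
- n = 52: noncentrality 0.40 × √52 = 2.884, power 80.8%.
- Enrolment: 52 / (1 − 0.20) = 65.

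Both figures are reproduced. There is no slack: 52 is the smallest n that reaches 80%.

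**2. Complete rows among the 52.** Expected number = 52 × (1 − m)^4, with power at the rounded n:

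| m per intermediate visit | (1 − m)^4 | Complete rows | d√n | Power |
|---|---|---|---|---|
| 0% | 1.000 | 52 | 2.884 | 80.8% |
| 2% | 0.922 | 48 | 2.771 | 77.5% |
| 5% | 0.815 | 42 | 2.592 | 71.6% |
| 10% | 0.656 | 34 | 2.332 | 62.0% |
| 20% | 0.410 | 21 | 1.833 | 41.5% |

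The power column is for the baseline-to-month-12 contrast in complete rows, before any Bonferroni correction. It is not the power of the omnibus test.

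**3. Bias under assumed drop-out mechanisms.** Simulation of 40,000 patients with six visits, correlation 0.7^|lag|, a true standardised 12-month change of −0.400, 20% drop-out and 5% random gaps at each intermediate visit. The mixed model here is maximum likelihood with unstructured covariance.

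| Drop-out depends on | Complete rows | Available baseline/month-12 pairs | Mixed model |
|---|---|---|---|
| nothing (completely at random) | −0.399 | −0.397 | −0.399 |
| the previous, observed score (at random) | −0.362 | −0.366 | −0.403 |
| the current, unobserved score (not at random) | −0.433 | −0.432 | −0.465 |

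Complete rows understate the improvement in the second case and overstate it in the third. The mixed model recovers the truth in the second. In the third it is further from the truth than complete rows.

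A separate simulation let drop-out (23%) depend on a poor earlier change in NPS. Complete rows gave −1.87 against a true −1.59, and the likelihood-based model gave −1.59. There too the data were missing at random by construction, so the model's recovery was to be expected. None of these mechanisms is taken from the protocol.

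**The case against.** **The 12-month contrast may lose nobody.** A missed month-3 visit does not destroy a baseline/month-12 pair. The pairwise comparisons are not restricted to patients with all six visits, and the study was sized on a paired t test. Run on available pairs, the contrast keeps all 52 and 80.8% power at unadjusted alpha. This stands: the power loss is conditional. It does not rescue the omnibus test, which is the method the protocol names for change over time.

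**This belongs in an analysis plan.** Missing-data rules and analysis sets often do, and their absence here is no finding. The point rests on the methods that the protocol itself chose.

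**Stronger readings that the documents do not support.**
- *A mixed model would remove the drop-out bias.* It does so only if data are missing at random and the model is adequate. Inefficacy, intolerance and adverse effects are listed as reasons for discontinuation, so informative drop-out is plausible.
- *The estimate must favour responders.* The direction depends on the mechanism, and the simulations go both ways.
- *The plan analyses a completers' set of 52, without those who stop for inefficacy.* The 52 is only the number expected after drop-out, and no analysis set is defined. Nor does the protocol say that NPS collection ends when the drug is stopped.

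**The replacement has its own weaknesses.** An unstructured covariance over six visits has 6 × 7 / 2 = 21 parameters, to be estimated from at most 65 patients. A Gaussian model also gives up the rank-based route for non-normal scores. Both objections are fair and are met in the fix.

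**Conclusion.** The concern holds in a limited form. The protocol ties NPS and the other scores to tests that, in their classical forms, discard a patient for one missed visit. It does so in a study where missed visits are likely and the sample size covers drop-out only.

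At assumed miss rates of 2% to 10% per intermediate visit, the omnibus test keeps about 48 down to 34 of the 52. If the 12-month contrast is held to the same rows, its power falls from 80.8% to between 77.5% and 62%. If it uses all available pairs, it does not fall for this reason. The protocol leaves that open. Bias is possible, but neither its size nor its direction can be derived from the documents.

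The method should be changed. The planned 52 and 65 stand.

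**What to change.** - **Main analysis.** Analyse NPS and the other scores with a linear mixed model for repeated measures: visit as a factor and unstructured covariance, with a small-sample degrees-of-freedom correction and a simpler covariance structure named in advance as fallback. Use every available visit of all enrolled patients.
- **Primary result.** Take the baseline-to-month-12 contrast in NPS with its 95% CI.
- **Informative drop-out.** Add a sensitivity analysis for patients lost because of inefficacy or adverse effects, for example multiple imputation with progressively less favourable values for them. A completers' analysis can be reported alongside but does not answer this question.
- **Non-normal scores.** Keep a rank-based paired test on all available baseline/month-12 pairs for clearly non-normal scores.

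The cost is a few sentences in the statistical section and slightly more analysis work in R, which is already specified. No new data and no larger sample are needed. The price is reliance on the missing-at-random and model assumptions, which the sensitivity analysis should probe.

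### The 80% power is for one unadjusted paired t-test, but the only stated analysis of NPS uses Bonferroni-corrected pairwise comparisons over six visits and does not exempt the primary 12-month contrast

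*Protocol*

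**What the plan says.** **Endpoint.** The protocol's Primary endpoint section sets one variable and one time point: "The primary endpoints will be the Improvement of NPS score (indicative of polyps score reduction) at 12 months after start of therapy".

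**Sample size.** The claim under Sample size calculation is: "a sample size of 52 patients achieves 80% power to reject the null hypothesis of zero effect size". It assumes a standardised effect of 0.40 and an alpha of 0.05, with no adjustment for multiplicity. The method is given as follows: "The sample size calculation was performed with a two-tailed Student's t test for paired data". The allowance for losses is: "Anticipating a 20% drop-out rate, 65 patients should be enrolled to obtain the final sample size of 52 subjects".

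**Visits.** The Procedures section has a baseline evaluation and asks centres for data from the "visits performed at 30 days since the beginning of therapy and at 3,6,9 and 12 months". With baseline, that makes six time points.

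**Analysis.** The Statistical Analysis section groups NPS with NCS, the VAS items, Sniffin' Sticks and SNOT-22. All of them go to a repeated-measures ANOVA or Friedman test, and the next sentence reads: "Correction for multiple pairwise comparisons will be performed by the Bonferroni test". The section does not say how many pairs are compared. It names no paired t-test for NPS, and it does not set the baseline-to-12-month contrast apart from the rest.

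**The concern.** The study is sized for one test and the analysis section describes another. An omnibus test over six visits asks whether NPS differs at any visit. It can be significant because of an early change that is lost by month 12, so it does not test the primary endpoint. Within the stated analysis, the 12-month answer can come only from the pairwise step, and that step is Bonferroni-corrected.

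If the primary contrast is corrected, it is judged at 0.05 divided by the number of comparisons, and the stated 80% no longer applies to it. If it is not corrected, the protocol should say so. As the text stands, the same 12-month result could be judged at 0.05, 0.01 or 0.0033, and the choice could be made after the data are seen.

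**Working it through.** **Inputs.** From Sample size calculation: n = 52 evaluable, d = 0.40, alpha = 0.05 two-sided, paired t-test, 20% drop-out. From Procedures: six time points. The protocol defines d as a mean difference over σ without saying which σ. I take it as the SD of the paired change, because that reading reproduces the stated 52.

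**Method.** Exact power of the paired t-test with df = n − 1 and noncentrality λ = d√n:

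power = P(T′ > t*) + P(T′ < −t*), where T′ is noncentral t (df, λ) and t* is the 1 − α/2 quantile of central t.

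Here df = 51 and λ = 0.40 × √52 = 2.884.

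**Step 1: reproduce the stated figure.** At α = 0.05, t* = 2.008 and power is 80.8%. With n = 51 it is 79.99%, so 52 is the smallest n reaching 80%. Enrolment is 52 / (1 − 0.20) = 65. Both figures are correct for a single unadjusted test.

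**Step 2: count the comparisons.** All pairs of six time points: 6 × 5 / 2 = 15. Each later visit against baseline only: 5.

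**Step 3: power of the 12-month contrast, n = 52, d = 0.40.**

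| 12-month contrast | Per-comparison α | t* | Power | Evaluable n for 80% | Enrolled (n / 0.8, rounded up) | d detectable with 80% at n = 52 |
|---|---|---|---|---|---|---|
| Tested alone | 0.05 | 2.008 | 80.8% | 52 | 65 | 0.396 |
| One of 5 against baseline | 0.05/5 = 0.01 | 2.676 | 58.5% | 77 | 97 | 0.490 |
| One of 15 pairs | 0.05/15 = 0.0033 | 3.080 | 43.2% | 94 | 118 | 0.547 |

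**Step 4: does the error term matter?** If the pairwise tests use the pooled ANOVA error (df = 5 × 51 = 255) with the same noncentrality, power is 61.4% for 5 comparisons and 47.0% for 15. For the Friedman branch the protocol names no pairwise test. A rough guide is a Wilcoxon signed-rank test at 95.5% efficiency, which means an effective n of 49 (0.955 × 52, rounded down). That gives 55.1% and 39.7%. The shortfall from 80% remains in every variant.

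**Step 5: dependence on the true effect.** At n = 52 with 15 pairs, power is 70% at d = 0.50, 81% at d = 0.55 and 89% at d = 0.60.

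**The case against.** The strongest defence is that the sample size section already names the primary test. It treats NPS as the primary outcome, specifies a two-sided paired t-test at 0.05, and the Primary endpoint section fixes month 12. On this view the repeated-measures analysis only describes the course of all the scores, the Bonferroni sentence belongs to that description, and the make-up of the comparison family can be left to a statistical analysis plan. This reading is possible, and under it power is 81%. But the Statistical Analysis section does not say it. That section lists NPS with the other scores under a single rule and exempts no contrast. The conflict is between statements the protocol itself makes, not a detail it has left open for later.

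A reader might go further and infer that the primary comparison has 43% power, so that a true effect of the planned size would be missed more often than found. The protocol does not support that as a flat statement. It gives no number of pairs, and 43% needs all 15 pairs and separate paired t-tests. With five comparisons against baseline, power is about 59%, and the effect would be found more often than missed.

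Two further points for the defence stand. Bonferroni makes the test stricter, so the risk is a missed effect and not a false claim. The loss also shrinks if the true effect exceeds 0.40. However, 0.40 is the protocol's own planning value, and the 80% claim rests on it.

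**Conclusion.** The concern holds in conditional form. The stated 80% belongs to one unadjusted paired t-test, and the only analysis the protocol states for NPS does not deliver it. If the baseline-to-12-month contrast is inside the Bonferroni family, its power is about 59% (5 comparisons) or about 43% (15 pairs). It is 81% only if the contrast is tested alone at 0.05.

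These figures assume 52 evaluable patients, a true standardised paired change of 0.40 and separate paired t-tests. Using pooled ANOVA error adds about 3 to 4 percentage points. The mismatch between the two sections is certain. Which of the power figures applies is not, because the protocol gives neither the size of the family nor the place of the primary contrast in it. It concerns the power statement for the primary endpoint, so it should be settled before analysis.

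**What to change.** In the Statistical Analysis section, state that the primary analysis is the paired change in NPS from baseline to month 12, tested once at two-sided alpha 0.05, reported with its 95% confidence interval and kept outside the Bonferroni family. Present the repeated-measures ANOVA or Friedman test and the other visit contrasts as secondary, with Bonferroni applied to those contrasts only. The 52 evaluable, 65 enrolled and 80% then stand. The cost is one or two sentences, with no extra patients or data.

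If the sponsor prefers to keep the primary contrast inside the correction, the protocol should state the number of comparisons and restate the power as about 59% (5) or about 43% (15). Alternatively, it could re-size to 77 evaluable (97 enrolled) or 94 evaluable (118 enrolled) respectively.

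### The predictor analysis is fixed as logistic regression of a clinical response although the endpoints are score improvements; modelling the score would keep information that a yes/no split discards

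*Protocol*

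**What the plan says.** The Endpoints section states: "The primary endpoints will be the Improvement of NPS score (indicative of polyps score reduction) at 12 months after start of therapy". SNOT-22, VAS for nasal obstruction, NCS, VAS for smell and Sniffin' Sticks are likewise listed as improvements of a score, with no threshold.

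The Sample size calculation keeps NPS as a quantity: "Considering NPS as a primary outcome a sample size of 52 patients achieves 80% power", "when the population effect size is 0.40 and the significance level (alpha) is 0.05", and "The sample size calculation was performed with a two-tailed Student's t test for paired data".

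In the Statistical Analysis section, change over time in NPS and the other scores "will be assessed by repeated measurement analysis of variance or Friedman's nonparametric test, as appropriate". For predictors, the outcome changes: "Potential predictors of clinical response at each time point will instead be assessed by univariable and multivariable logistic regression models". The section names the R package (rms) and takes predictor scores from the visit before. The Procedures section asks centres for "visits performed at 30 days since the beginning of therapy and at 3,6,9 and 12 months", so there are up to five time points. The protocol does not tie clinical response to a particular score or cut-off.

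**The concern.** Score endpoints, a sample size built on a score and a repeated-measures analysis of scores all treat the outcome as a quantity. The predictor models then move to a response, and logistic regression of a response ordinarily means a yes/no outcome.

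Splitting a score puts a patient who just reaches the cut with one who improves greatly, and separates patients one point apart. In a cohort of about 52 evaluable patients that loss matters: real predictors are more likely to be missed, and the results depend on where the cut lies. The concern is with the outcome and model type of this one analysis, not with its list of predictors.

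**Working it through.** **1. The plan's own figure.** Inputs from the Sample size calculation: d = 0.40, two-sided alpha 0.05, paired t test, 20% dropout. At n = 52 the noncentrality is 0.40 × √52 = 2.884 on 51 degrees of freedom, giving power of 80.8%. At n = 51 power is 79.99%, just short of 80%. Dropout: 52 / (1 − 0.20) = 65. Both figures reproduce and are not in dispute.

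**2. Information kept after a split.** For a normal score split at standardised cut z, with response rate p, the efficiency relative to the score itself is φ(z)² / [p(1 − p)]. At p = 0.50 this is 2/π = 0.637. The response rate is not in the protocol, so a range is shown:

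| Response rate | Information kept | Loss | Effective n (of 52) |
|---|---|---|---|
| 50% | 0.637 | 36% | 33 |
| 70% | 0.576 | 42% | 30 |
| 80% | 0.490 | 51% | 25 |
| 90% | 0.342 | 66% | 18 |

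The first row is the smallest loss for a normal score.

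**3. Allowing for a coarse score.** If the change is rounded to whole points and compared with the rounded score, the better of a 1-point or 2-point cut keeps between 0.687 (SD 1.0, mean change 0.4) and 0.629 (SD 1.0, mean change 1.0 or 2.0). SDs of 1.5 to 2.5 fall between these. The loss at a central cut is therefore about 31% to 37%. Less central cuts lose more: at SD 2.0 and mean change 2.0, a 1-point cut keeps 0.528, a loss of 47%.

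**4. What this means for NPS under the plan's d.** Assumptions: SD of change 2 points (range 1.5 to 2.5; none is given in the protocol), mean change 0.40 × 2 = 0.8, rounding to whole points. Then P(change ≥ c) = 1 − Φ((c − 0.5 − 0.8)/2), and the information kept is the formula of step 2:

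| Cut | Responders (SD 2) | SD 1.5 to 2.5 | Events in 52 (SD 2) | Information kept (SD 2) |
|---|---|---|---|---|
| ≥ 1 point | Φ(0.15) = 56% | 53-58% | 29 | 63% |
| ≥ 2 points | 1 − Φ(0.35) = 36% | 27-42% | 19 | 61% |
| ≥ 3 points | 1 − Φ(0.85) = 20% | 10-27% | 10 | 49% |

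**5. Power to detect one predictor, n = 52.** Simulated cohorts, SD 2, linear test of the score against the likelihood-ratio test from logistic regression. The predictor correlations are assumed.

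- Correlation 0.40, three separate sets of runs: 85%, 84% and about 83% with the score. With logistic regression at cuts of 1, 2 and 3 points: 67%, 66%, 54%; 67%, 67%, 57%; and 66%, 64%, 56%.
- Correlation 0.35, two sets: 73% and 71% with the score, against 54%, 54%, 44% and 53%, 53%, 44%.
- Correlation 0.376 (about 80% power with the score), with response rates of 50%, 70% and 80% set directly: 61%, 57% and 49% with logistic regression.

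**The case against.** Four arguments deserve weight.

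*The missing definition belongs to the SAP.* Only the protocol is available. A responder cut-off for a supporting regression is commonly left to the SAP, so its absence is not the fault here. A reader might go further and infer that the cut-off will be picked once 12-month scores are known, because the retrospective cohort runs from 01 March 2023. The protocol does not support that: it does not say when a cut-off is set or how many retrospective patients have reached 12 months. What stands without it is the choice of model, which the protocol does fix and which a later cut-off would not repair.

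*Nothing says that a score will be split.* This is correct. The rms package also fits ordinal logistic models, and response could be a composite of scores, surgery and steroid use. The endpoints include yes/no items too, such as discontinuation and need for FESS or systemic steroids, though none is called clinical response. Splitting a score is the ordinary reading, not stated text. Under a composite, the loss figures above would not apply as they stand.

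*The endpoints are analysed correctly elsewhere.* Also correct. NPS and the other scores are tested as scores, and finding predictors is not among the stated objectives. A reader might infer that the plan contradicts its own endpoint, or that the whole study loses over a third of its information. Neither follows: the loss is confined to this analysis, and with a coarse score it can be slightly under a third.

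*Which patients respond is a fair clinical question.* It is, and a responder analysis can stay. It need not be the main predictor analysis in so small a sample.

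**Conclusion.** The point holds as a recommended improvement to a supporting analysis. The protocol commits the predictor analysis to logistic regression of a response that is not one of its endpoints, while a model of the score would answer the predictor question for the actual endpoint with more power from the same patients.

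If a score is split, the loss is about 31% to 37% at a central cut and larger elsewhere. With an SD of change of 2 points and a predictor correlation of 0.40, both assumed, power drops by roughly 17 to 31 percentage points (84 − 67 = 17 at the least, 85 − 54 = 31 at the most, within the same set of runs). Other SDs act mainly by shifting the response rate, whose effect on the loss is tabulated above.

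**What to change.** In the Statistical Analysis section, make the main predictor analysis a linear or proportional-odds regression (ols or orm in rms) of the NPS score at each visit, with 12 months as the principal one, adjusted for baseline NPS. Treat the other scores the same way. The use of predictor scores from the preceding visit can remain.

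If a responder analysis is still wanted, label it secondary or descriptive, and fix its score and cut-off before outcome data are examined.

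The cost is a wording change, with no new patients, data or software. The small downside is that results appear as score differences or proportional-odds ratios, which clinicians know less well than odds ratios for response.
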